## 8.4 Study Termination

The whole study may be discontinued at the discretion of the investigator in the event of any of the following:

- Occurrence of AEs not seen previously which by virtue of their nature, severity and duration are considered to necessitate study termination.
- Hematologic adverse events criteria for study termination
  - >2 events of grade  $\geq 3$  thrombocytopenia or neutropenia in the first 10 subjects
  - >3 events of grade  $\geq 3$  anemia in the first 10 subjects
 Medical or ethical reasons affecting the continued performance of the study.
- Bayer is unable to provide radium-223 for the subject.
- Dendreon is unable to manufacture sipuleucel-T in >2 of first 10 patients.
- Difficulties in the recruitment of patients.

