## Amendment Rationale

The quantification of radium-223 radioactivity in Xofigo® is based on the primary standardization performed by the US National Institute of Standards and Technology (NIST). The NIST Standard Reference Material is used to calibrate the instruments in production and quality control of both the drug substance and drug product. Additionally, the calibrated instruments in production at the Institute for Energy Technology (IFE, Norway) are used to prepare the NIST traceable radium-223 reference material, which are then sent to the treatment sites (e.g., nuclear medicine laboratory physicians or technicians) for dial setting of their dose calibrators, to allow verification of the patient dose. A reassessment of the primary standardization was initiated by the NIST. A discrepancy of approximately 10% between the published NIST primary standardization (Cessna, 2010, NIST 2010) and current measurements was confirmed and a revised NIST primary reference standard has been issued (Zimmerman, 2015, NIST update). As a result of the revised NIST primary standardization, an adaption of the numerical description of patient dose and the description of radioactive concentration of the drug product solution becomes necessary. This concerns Xofigo® for commercial use and product used in clinical trials.

After the implementation of the new standard (NIST update) the numerical description of the patient dose will be adjusted from 50 kBq/kg to 55 kBq/kg, and the numerical description of the radioactivity in the vial will be changed from 1,000 kBq/mL to 1,100 kBq/mL

The values in this protocol have been revised as per the United States National Institute of Standards and Technology (NIST) standardization update.

Bayer has submitted a variation application to the FDA. The current standard (NIST 2010), dial setting and dose will remain in effect for this study until Bayer has confirmed the unique implementation date in the 2nd quarter of 2016 as agreed with FDA and notified the **Principal Investigator and IND Sponsor:**

[name]  
The Sidney Kimmel Comprehensive Cancer  
[name]  
[name]

Version 4.0 Date: 08/21/2020

NCT02463799

The values for radium-223 in this protocol has been revised as per the US NIST standardization update (agreed on 17 Mar 2015)

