### **5.7.4 Study Termination**

The whole study may be discontinued at the discretion of the investigator in the event of any of the following:

- Occurrence of AEs not seen previously which by virtue of their nature, severity and duration are considered to necessitate study termination.
- Hematologic adverse events criteria for study termination
  - $>2$  events of grade  $\geq 3$  thrombocytopenia or neutropenia in the first 10 subjects
  - $>3$  events of grade  $\geq 3$  anemia in the first 10 subjects
- Medical or ethical reasons affecting the continued performance of the study.
- Bayer is unable to provide radium-223 for the subject.
- Dendreon is unable to manufacture sipuleucel-T in  $> 2$  of first 10 patients.

Version 4.0 Date: 08/21/2020

NCT02463799

The values for radium-223 in this protocol has been revised as per the US NIST standardization update (agreed on 17 Mar 2015)

- Difficulties in the recruitment of patients.

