## 7.3 Adverse Events Reporting

The principal investigator will notify the appropriate regulatory agencies of any SAEs occurring during the study period, regardless of causality. These agencies include the Sidney Kimmel Comprehensive Cancer Center (SKCCC) Data and Safety Monitoring Committee (DSMC), and the Institutional Review Board (IRB) and the Institutional Biosafety Committee (IBC) of the Johns Hopkins Medical Institutions (JHMI). The representatives of Dendreon will also be notified. Expedited reporting to the PI within 24 hours is required for all SAEs (see Section 7.4.1). For SAEs that are fatal, life-threatening, or treatment-related but non-life threatening: IRB/IBC reporting by the PI is required within 3 days. For unrelated SAEs, IRB/IBC reporting

by the PI is required within 15 days. All other AEs should be documented on CRFs and submitted according to the standard data management guidelines.

Adverse event information will be collected continuously throughout the duration of the study. Participants will be instructed to notify their treating provider of any new signs or symptoms, and providers will actively assess patients for adverse events at each visit (including by evaluation of laboratory studies). The investigator will assess each AE for its severity and for its relationship to the study drug, and all events Grade 1 or higher will be documented on CRFs and then reported as described above within the required time frame. Any AE occurring while a patient is on study (*i.e.* after informed consent has been signed) or within 30 days of study termination requires reporting. AEs occurring later than this must still be reported if a causal relationship with the study drug is suspected.

For all AEs, the investigator must pursue and obtain information to adequately determine the causality and outcome of the event, and to assess whether it meets criteria for a SAE. In addition, follow-up of an AE is required until the event either resolves or stabilizes.

The principal investigator must keep copies of all CRFs and other AE information, including correspondence with the IRB and/or FDA, for as long as required to comply with national and international regulations.

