#### Bayer

Attn: Global Pharmacovigilance - USA  
Email: [[contact]](mailto:[contact])  
[contact]  
Address:  
Mail only: Bayer HealthCare  
[name]  
Address: [name]  
FDX or UPS only [name] for UPS

Reports for all Bayer products can also be phoned in via our Clinical Communications Dept:  
[contact]

The initial report for each SAE or death to the Study Coordinator should include the following information:

- name and contact information of the reporter
- protocol # and title
- patient identified by one or more of the following:
  - patient initial
  - patient identification number
  - knowledge that a patient who experienced the adverse event exists
  - age
  - sex
- date the event occurred
- description of the SAE

Version 4.0 Date: 08/21/2020

NCT02463799

The values for radium-223 in this protocol has been revised as per the US NIST standardization update (agreed on 17 Mar 2015)

- investigational agent(s) received (and dose level) at the time the SAE occurred
- time from administration of the investigational agent(s) to start of the event
- description of the patient's condition

Follow-up information including severity, causality, action taken, concomitant medications, and outcome should be communicated to the principal investigator as soon as possible with an indication whether an amendment will need to be made to the protocol, the consent form, or both, as a result of this event.

The Investigator may report serious adverse drug reactions (SADRs) using either:

An ADEERS form (Adverse Event Expedited Reporting System) available at <http://ctep.cancer.gov/reporting/adeers.html>

OR

A MedWatch form available at <http://www.fda.gov/medwatch/>

The report of SAE to Dendreon should be made using an SAE Report Form provided by Dendreon (Appendix 3). Significant new information regarding an ongoing SAE and the resolution must be sent to Dendreon within 3 business days of awareness of the new information to Dendreon on the SAE Report Form.

Sponsor investigator shall notify institution, co-investigators and IRB immediately during the conduct of the study and/or after the study is completed should it become aware of information related to the study that would impact participant safety or clinical care. Institution shall promptly disclose such information to study participants.

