#### **8.7 Interim Analyses**

Version 4.0 Date: 08/21/2020

NCT02463799

The values for radium-223 in this protocol has been revised as per the US NIST standardization update (agreed on 17 Mar 2015)

We will carry out interim safety assessments with statistical monitoring. We will monitor patients in groups of 10 (5 per treatment arm). The formal monitoring rule relates to the risk of hematologic adverse events. Specifically, we will monitor thrombocytopenia, neutropenia, and anemia.

- >2 events of grade  $\geq 3$  thrombocytopenia or neutropenia in the first 10 subjects
- >3 events of grade  $\geq 3$  anemia in the first 10 subjects

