## **10.5 Study Monitoring and Quality Assurance**

This is a DSMP Level I study under the SKCCC Data Safety Monitoring Plan (12/6/2012). *The SKCCC Compliance Monitoring Program will provide external monitoring for JHU-affiliated sites in accordance with SKCCC DSMP (Version 6.0, 02/21/2019). The SMC Subcommittee will determine the level of patient safety risk and level/frequency of monitoring.*

The Clinical Research Office will perform an audit after the first subject has been treated and then periodically depending on the rate of accrual and prior audit results. All trial monitoring and reporting will be reviewed annually by the SKCCC Safety Monitoring Committee.

The PI is responsible for internally monitoring the study. Data must be reviewed to assure the validity of data, as well as, the safety of the subjects. The PI will also monitor the progress of the trial, review safety reports, and clinical trial efficacy endpoints and to confirm that the safety outcomes favor continuation of the study.”

Contact the CRO QA Office ([contact]) with questions.

Version 4.0 Date: 08/21/2020

NCT02463799

The values for radium-223 in this protocol has been revised as per the US NIST standardization update (agreed on 17 Mar 2015)

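### Crossing a haematologic safety limit triggers no required action; stopping is left to the investigator's discretion

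*Combined protocol and SAP*

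**What the plan says.** Section 8.7 plans interim safety assessments with statistical monitoring, in groups of 10 subjects with 5 per arm. It states that "The formal monitoring rule relates to the risk of hematologic adverse events" and gives two limits for the first 10 subjects: more than 2 events of grade 3 or higher thrombocytopenia or neutropenia, and more than 3 events of grade 3 or higher anaemia. The section ends there.

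Sections 5.7.4 and 8.4 repeat the limits under the label "Hematologic adverse events criteria for study termination". The sentence governing the whole list is "The whole study may be discontinued at the discretion of the investigator in the event of any of the following". The same sentence covers supply problems and slow recruitment. The title material that runs into the Amendment Rationale gives a single role, "Principal Investigator and IND Sponsor".

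Other oversight is described elsewhere:

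- **7.3:** all SAEs go to the cancer center's DSMC, the IRB and the IBC. They reach the principal investigator within 24 hours. Fatal, life-threatening or treatment-related SAEs go to the IRB and IBC within 3 days.
- **7.4.1:** for information bearing on participant safety, "Sponsor investigator shall notify institution, co-investigators and IRB immediately during the conduct of the study".
- **10.5:** "This is a DSMP Level I study under the SKCCC Data Safety Monitoring Plan". An SMC subcommittee sets the level and frequency of monitoring, the Safety Monitoring Committee reviews annually, and the principal investigator is to confirm that safety supports continuing.
- **5.7.3:** a man whose toxicity would call for a lower radium-223 dose, or whose treatment is delayed by more than four weeks, comes off radium-223.

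**The concern.** A monitoring limit protects subjects only if something follows when it is crossed. Here the limits are called formal in one section and termination criteria in two others, yet the only stated consequence is that the investigator may stop. That discretion most naturally rests with the principal investigator, who is also the IND sponsor. The protocol requires no registration hold, no referral and no decision by anyone independent.

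Safety of the combination is a secondary clinical objective, and these are the only numeric toxicity limits in the plan. If one is exceeded, further men can be randomized to radium-223 plus sipuleucel-T while the protocol's own criterion stands breached and no outside body has been asked to decide anything.

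This point is separate from which arm the limits count, how many subjects they cover, and which laboratory results reach the adverse event form.

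**Working it through.** **Step 1: does any section attach a required action to a crossing?**

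| Section | What it provides | Tied to the limits? |
|---|---|---|
| 8.7 | Limits, reviewed in groups of 10 | States limits, no action |
| 5.7.4, 8.4 | Limits as termination criteria | Yes, but permissive only |
| 7.3 | SAE reporting, event by event | No |
| 7.4.1 | Immediate notice of safety-relevant information | No, and no decision required in return |
| 10.5 | Annual committee review; PI's general duty | No |
| 5.7.3 | One man's radium-223 treatment | No, does not govern registration |

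None does. The protocol states no operating characteristics for the limits, so there is no figure of its own to reproduce.

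**Step 2: how many men could be registered after a crossing?**

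Planned enrolment is 34 (8.2) or up to 33 (synopsis). After the first 10: 34 − 10 = 24, or 33 − 10 = 23. With 1:1 allocation about 12 of these receive radium-223. This is a ceiling.

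The radium-223 infusions run from week 0 to week 20 (6.1). Suppose a crossing occurs 20 weeks after the tenth registration, with accrual of r men per month (both assumed) and 4.348 weeks per month. Men still to register = 24 − r × 20/4.348:

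| r per month | 1 | 2 | 3 | 4 |
|---|---|---|---|---|
| Still to register | 19.4 | 14.8 | 10.2 | 5.6 |

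**Step 3: how likely is a crossing?**

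Assume at most one event per man and a true event rate p; neither comes from the documents. X is the number of men with an event. Three cases:

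- (a) all 10 men share p: X ~ Bin(10, p)
- (b) only the five radium-223 men are at risk: X ~ Bin(5, p)
- (c) five radium-223 men at p, five Arm 2 men at 5%: X ~ Bin(5, p) + Bin(5, 0.05)

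| Limit | Case | p = 10% | p = 20% | p = 30% |
|---|---|---|---|---|
| X > 2 | (a) | 0.070 | 0.322 | 0.617 |
| X > 2 | (b) | 0.0086 | 0.058 | 0.163 |
| X > 2 | (c) | 0.033 | 0.114 | 0.241 |
| X > 3 | (a) | 0.013 | 0.121 | 0.350 |
| X > 3 | (b) | 0.0005 | 0.0067 | 0.031 |
| X > 3 | (c) | 0.004 | 0.023 | 0.068 |

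These are chances of crossing a limit, not of stopping, because no action is fixed.

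**Step 4: what would a hold cost?**

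Registrations delayed = r × days/30.44. For r from 1 to 4, a 14-day hold delays 0.5 to 1.8 and a 30-day hold delays 1.0 to 3.9.

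**The case against.** The best case for leaving the text alone has four parts.

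- **Purpose and decision-maker are named.** Sections 5.7.4 and 8.4 label the limits as termination criteria and say who decides. What is missing is compulsion, and investigator discretion is a tenable choice in a 34-man phase 2 study. This stands as far as termination goes, and nothing here asks for automatic stopping. It does not explain why a crossing requires no hold and no outside look.
- **The institutional monitoring plan may already cover it.** Section 10.5 places the trial under that plan, which is not among the documents. It may well contain a hold or an off-cycle review. This also stands, and it limits the finding to what the protocol itself states. If the process exists, a cross-reference is enough.
- **Oversight between annual reviews is real.** Section 7.4 gives blood dyscrasias as an example of events that may be judged serious, so some grade 3 or higher cytopenias could enter the SAE route with its 24-hour and 3-day deadlines. The group-of-10 assessments fall during accrual, and the principal investigator's duty under 10.5 would plainly be engaged. All true, but SAE reports arrive singly and no recipient is asked to act on a cumulative count.
- **A crossing may be unlikely.** Section 1.2.2 reports no clinically meaningful difference in grade 3 and 4 haematologic events between radium-223 and placebo, and serious anaemia in 8% against 9%. Seriousness is not grade, and that was monotherapy. Still, taking 8% for all 10 men gives P(X > 3) of about 0.006. The highest figures in the table need a 30% rate in both arms, which nothing in the documents supports. This argues for modest expectations of benefit. It also means the hold would seldom be used.

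**Conclusion.** The concern holds. The protocol calls the haematologic limits a formal rule and lists them as termination criteria, but requires nothing when one is crossed. Followed exactly, it allows up to 24 more men (23 by the synopsis) to be registered after a crossing without any required independent decision.

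The textual finding rests on no assumption. The sizes do: accrual of 1 to 4 per month, a crossing at 20 weeks, one event per affected man, and event rates of 10% to 30%. Under these, about 6 to 19 men would remain to be registered. The chance of crossing the first limit runs from about 1% to 62%, and the second from about 0.05% to 35%.

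The plan does not lack safety review, and no analysis or power figure is affected. This is a change that should be made because it improves subject protection cheaply. Confidence is medium, because the institutional monitoring plan could not be seen.

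**What to change.** Add to 8.7, with matching edits in 5.7.4 and 8.4, text to this effect:

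> If a haematologic limit is crossed, registration of new subjects is held and haematologic data by arm are sent at once to the SKCCC safety committee (SMC or DSMC, as the SKCCC Data Safety Monitoring Plan allows) for an unscheduled review within a stated period, for example 14 to 30 days. Registration resumes only on that committee's written decision.

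If the monitoring plan already has such a process, cite it in 8.7 and name these limits as its trigger. Termination stays a matter of judgement, discretion remains for the other listed grounds, and men already on treatment continue under 5.7.2 and 5.7.3.

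The cost is a one-paragraph amendment using an existing committee and data already collected. The sponsor must first confirm that the monitoring plan lets the committee act this way. Nothing further is spent unless a limit is crossed. Then it is one off-cycle review and about 0.5 to 4 delayed registrations at 1 to 4 per month. A hold could also fall when the true event rate is acceptable: if 10% is taken as acceptable, the first limit would trigger it about 7% of the time when all 10 men share that rate, and about 1% when only the five radium-223 men are at risk. Sample size, power and the primary analysis are unchanged.

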## 8.5 Endpoints

### 8.5.1 Primary Endpoints

- Peripheral PA2024-specific T-cell proliferation using a tritiated thymidine ( $^3\text{H}$ -thymidine) incorporation assay at week 6 after the first sipuleucel-T infusion in each arm reported as stimulation index (SI), defined as  $^3\text{H}$ -thymidine incorporation in the presence of PA2024 antigen divided by  $^3\text{H}$ -thymidine incorporation with media alone.

### 8.5.2 Secondary Endpoint(s)

#### 8.5.2.1 Secondary Immune Endpoint(s)

- The mean peripheral PA2024-and PAP-specific T-cell proliferation using a  $^3\text{H}$ -thymidine incorporation assay reported as SI at baseline and 6, 10, 14, 26, 39, and 52 weeks after the first infusion of sipuleucel-T.
- The mean peripheral PA2024-and PAP-specific T-cell activation to sipuleucel-T using interferon gamma ( $\text{IFN}\gamma$ ) enzyme-linked immunosorbent spot (ELISPOT) at baseline and weeks 6, 10, 14, 26, 39, and 52 weeks after the first infusion of sipuleucel-T.

Version 4.0 Date: 08/21/2020

NCT02463799

The values for radium-223 in this protocol has been revised as per the US NIST standardization update (agreed on 17 Mar 2015)

- The mean PA2024-and PAP-specific antibody (IgM and IgG) response to sipuleucel-T using enzyme-linked immunosorbent assay (ELISA) at baseline and weeks 6, 10, 14, 26, 39, and 52 weeks after the first infusion of sipuleucel-T.
- Product immune parameters including CD54 + cell counts and upregulation and total nucleated cell (TNC) counts.

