## Statistical Considerations

The study is designed to test the null hypothesis of no difference in immune response to sipuleucel-T evaluated on the basis of PA2024-stimulated T cell proliferation via H-thymidine uptake between sipuleucel-T alone and sequential administration of radium-223.

For primary endpoint, PA2024-specific H-thymidine uptake was selected because it has demonstrated the highest signal to noise ratio and showed the strongest correlation with OS of all cellular and humoral assays evaluated in prior studies of sipuleucel-T.

With 15 subjects in each arm, we seek to detect a 3.6-fold difference between the arms with 80% power in mean SI of PA2024-specific H-thymidine uptake at week 6 after the first infusion of sipuleucel-T

The immune response population will consist of all subjects who receive 3 infusions of sipuleucel-T and at least 4 infusions of radium-223.

The intent-to-treat population is defined as all randomized subjects, regardless of whether they receive treatment. Analysis of non-immune response efficacy endpoints will be performed using this analysis population.

The safety population will include all subjects who undergo at least 1 leukapheresis procedure or receive at least 1 dose of radium-223.

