### **5.2.3 Product Quality assessment**

Prior to infusion, small samples (3% to 4%) of cellular components from pre and post-culture (PA2024) cells will be used to assess product potency as part of the normal sipuleucel-T manufacturing process. Sipuleucel-T quality assessments include total TNC count, CD54+ cell count and CD54 upregulation.

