### **5.2.5 Sipuleucel-T Product Failures and Leukapheresis Rescheduling**

In the event that a subject's leukapheresis procedure fails, sipuleucel-T does not meet quality release specifications, or infusion is not possible for any other reason, the subject may be scheduled to undergo a repeat leukapheresis procedure. A minimum of 2 days must have elapsed since the last leukapheresis procedure. Scheduling will depend upon capacity of the leukapheresis and Dendreon manufacturing facilities. If the second or third leukapheresis appointment is delayed or rescheduled for any reason, a physical examination and all other pre-leukapheresis procedures must be repeated within the 5 days prior to the next leukapheresis procedure.

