### 8.3 Populations for Analyses

The immune response population will be defined as subjects who receive 3 infusions of sipuleucel-T and 2 infusions of radium-223. Analysis of immune response endpoints, including

Version 4.0 Date: 08/21/2020

NCT02463799

The values for radium-223 in this protocol has been revised as per the US NIST standardization update (agreed on 17 Mar 2015)

the primary endpoint, will be performed using this population. This population will also be used to perform supplementary analyses of non-immune response efficacy endpoints.

The safety population will include all subjects who receive at least 1 leukapheresis procedure or receive at least 1 dose of radium-223. All safety variables (e.g., AEs, laboratory data, and vital sign data) will be analyzed based on the safety population.

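### Product quality is a secondary endpoint, but on the plainest reading of Section 8.3 men whose failed products are not replaced leave its analysis

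*Combined protocol and SAP*

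**What the plan says.** Evaluating the sipuleucel-T product immune parameters is a secondary immune objective (Section 2.2.1). Section 8.5.2.1 lists the endpoint as "Product immune parameters including CD54 + cell counts and upregulation and total nucleated cell (TNC) counts".

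Section 8.3 defines the analysis set: "The immune response population will be defined as subjects who receive 3 infusions of sipuleucel-T and 2 infusions of radium-223". It then assigns endpoints to it: "Analysis of immune response endpoints, including", the sentence continuing "the primary endpoint, will be performed using this population". The synopsis has a different radium-223 condition: "The immune response population will consist of all subjects who receive 3 infusions of sipuleucel-T and at least 4 infusions of radium-223". Both versions require 3 sipuleucel-T infusions.

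Section 5.2.3, on testing before infusion, says: "Sipuleucel-T quality assessments include total TNC count, CD54+ cell count and CD54 upregulation". Section 5.2.5 covers the case where "sipuleucel-T does not meet quality release specifications", together with failed leukapheresis and any other reason that prevents infusion. In those cases "the subject may be scheduled to undergo a repeat leukapheresis procedure".

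Section 6.3 starts sipuleucel-T in Arm 1 after the second radium-223 dose. The Arm 1 schedule puts the first pre-leukapheresis visit at week 6, after radium-223 at weeks 0 and 4.

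No section names a separate analysis set for product parameters, says whether failed or repeat products are included, or says how several products from one man are combined.

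**The concern.** Whether a man receives 3 infusions depends partly on whether his products pass release, and the endpoint consists of the measures used to judge product quality. Restricting the endpoint to men with 3 infusions therefore selects on the endpoint itself, after randomisation.

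This would matter less if selection worked equally in both arms. Here it may not: Arm 1 collections follow radium-223 and Arm 2 collections do not. If radium-223 lowers cell counts, more Arm 1 products fall below the release limit, more low-count Arm 1 men are removed, and the Arm 1 men who remain look closer to Arm 2. A reader of the results could then take product quality to be less affected than it was. The protocol treats manufacturing failure as important: inability to manufacture in more than 2 of the first 10 patients is a possible ground for stopping the study (Sections 5.7.4 and 8.4).

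**Working it through.** **Plan's own figure.** None is stated for this endpoint. The primary sample size reproduces and is not affected: n = 2(1.645 + 0.842)² × 1.4² / (ln 3.6)² = 2 × 6.18 × 1.96 / 1.641 = 14.8, so 15 per arm.

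**Who leaves the set.** Putting Sections 8.3, 5.2.3 and 5.2.5 together gives three cases.
- All three products pass: the man is in.
- A product fails and a repeat succeeds: the man is in, but the plan is silent on whether the failed value counts.
- A product fails and is not replaced: the man is out, and all his product values go with him.

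**How much repeats help.** The documents give no failure rate. Assume independent per-product failure f.
- No repeat, share of men left with fewer than 3 infusions, 1 − (1 − f)³: 5.9%, 14.3%, 27.1% and 38.6% for f = 2%, 5%, 10% and 15%.
- One repeat per dose, 1 − (1 − f²)³: 0.1%, 0.7%, 3.0% and 6.6%.

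Independence flatters the repeat, because a man with persistently low counts is likely to fail again. The next step allows for that.

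**Effect on an arm ratio (all inputs assumed).** Log count = arm mean + man effect (SD 0.4) + product effect (SD 0.3), so total SD = √(0.16 + 0.09) = 0.5. Three products per man. True Arm 1/Arm 2 ratio 0.70, so the Arm 1 mean is ln 0.70 = −0.357. The release limit L is set so that a fraction f of Arm 2 products miss it: L = 0.5 × z_f. Arm 1 product failure is then Φ((L + 0.357)/0.5):
- f = 3%: L = −0.940, Arm 1 failure Φ(−1.17) = 12%.
- f = 10%: L = −0.641, Arm 1 failure Φ(−0.57) = 28%.

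Simulation with 400,000 men per arm, keeping only men who reach 3 released products:

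| Arm 2 product failure | Repeat | Men excluded, Arm 1 | Men excluded, Arm 2 | Observed ratio (true 0.70) |
|---|---|---|---|---|
| 0.5-1% | one per failed product | 2-4% | 0.2-0.5% | 0.72-0.73 |
| 3-10% | one per failed product | 11-29% | 2-8% | 0.76-0.82 |
| 3-10% | none | 23-47% | 7-20% | 0.78-0.83 |

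Share of the 30% loss hidden, (observed − 0.70)/0.30: about 6-10%, 21-40% and 26-43% for the three rows. If failed products of retained men are also counted, the middle row becomes 0.75-0.80, so counting them without bringing back the excluded men corrects only part of the bias. If radium-223 had no effect on counts, both arms would be selected alike and the ratio would stay at 1.

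**Comparison with the plan's allowance.** The plan allows for 3 of 33 (9.1%, synopsis) or 4 of 34 (11.8%, Section 8.2) non-evaluable men for all reasons. With 17 per arm, the no-repeat row loses 17 × (0.235 + 0.068) = 5 to 17 × (0.474 + 0.199) = 11 men to product failure alone. The one-repeat row at 3-10% loses 17 × (0.107 + 0.02) = 2 to 17 × (0.29 + 0.08) = 6. The no-repeat row is therefore harsher than the sponsor planned for.

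**Check without assumed SDs.** If the men lost are those with the lowest values of a normally distributed measure, losing a fraction p of an arm raises its mean by φ(z_p)/(1 − p) SD: 0.18, 0.23 and 0.35 SD for p = 9%, 12% and 20%. These are upper-end values, since not every loss is a product failure.

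**The case against.** The strongest answer is that the plan never says product parameters are analysed only in men with 3 infusions. Section 6.10.1 lists the immune response assessments as ELISPOT, thymidine uptake and ELISA, and leaves product measures to Section 6.10.3, whose one stated use is correlation with clinical outcome. Section 8.6.3 names no clear between-arm test for them. That stands in part: the restriction is an inference from the endpoint heading and Section 8.3. But no other set is named, so if the sponsor intended something else, the same sentence is still needed.

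A reader might infer that every man with a failed product drops out. Section 5.2.5 does not support that: a repeat is allowed, and Section 8.6.5 tabulates up to 5 or more leukaphereses. Only men whose failure is not made good are lost.

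A reader might also infer that the plan hides manufacturing harm altogether, or that this endpoint is the trial's designated test of it. Neither is supported. Section 8.6.5 reports infusion counts, leukapheresis counts and reasons for not completing 3 infusions, and the objective is only to evaluate the parameters. However, Section 8.6.5 does not promise a layout by arm, and it does not return failed-product values to the endpoint.

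Finally, the release specifications are not in the documents, and Section 5.2.5 also covers failed collections and other causes, so not every loss is selection on these three measures. That stands. The link is close all the same: the synopsis gives a minimum of 50 million antigen presenting cells per dose, and Section 1.2.1 defines these as large CD54-positive cells.

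**Conclusion.** The point holds in a limited form. On the plainest reading, the product-quality endpoint is analysed in a set whose membership depends partly on product quality, and the plan does not say how failed and repeat products of retained men are handled. If radium-223 lowers these measures, any arm comparison is biased towards no difference.

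The direction follows from the mechanism, provided failure means falling below a lower limit. The size does not follow from the documents. It rests on assumed SDs, failure rates and a 30% true loss, and on counts rather than CD54 upregulation. Across the scenarios examined it runs from slight (0.72 for a true 0.70, where failure is rare and repeats are done) to material (0.83, where failure is common and no repeat is done). None of these figures should be quoted as an expected bias for this trial.

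The primary endpoint's sample size and power are unaffected. This is a secondary endpoint without a clearly specified arm test. The correction is worth making mainly because it is cheap and gives an arm-level picture of product quality that the 3-infusion set cannot give.

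**What to change.** In Section 8.3, give product immune parameters their own set: all subjects with at least 1 leukapheresis, by randomised arm. Keep the 3-infusion set for the peripheral immune assays.

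In Section 8.6.3, state that TNC count, CD54+ count and CD54 upregulation will be summarised by arm and collection number, using every product with a measured value, including products that failed release and repeat collections. Report the release-failure rate by arm, and the number of men per arm who had no leukapheresis.

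While Section 8.3 is open, reconcile its radium-223 condition (2 infusions) with the synopsis (at least 4), and say that it applies to Arm 1 only. Read literally, no Arm 2 subject could meet it.

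Cost: a sentence or two in each section, with no new sampling, because the assessments are part of normal manufacturing (Sections 5.2.3 and 6.10.3). Failed-product values must be requested from the manufacturer. Some failed collections may have no post-culture value; these should be counted and reported as such, by arm.
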